### **6.1.2 Formulation, Appearance, Packaging, and Labeling**

Ferumoxytol injection is available in single use vials in the following package sizes:

**Table 3: Feraheme Packaging Description**

| NDC Code  | Dose / Total volume per vial | Vials / Carton |
|------------------|-------------------------------------|-----------------------|
| NDC 59338-775-01 | 510 mg/ 17 mL                       | 1                     |
| NDC 59338-775-10 | 510 mg/ 17 mL                       | 10                    |

CONFIDENTIAL

This material is the property of the NYU School of Medicine and Langone Medical Center. Do not disclose or use except as authorized in writing by the study sponsor  
Interventional Template Version: 28 APR 2017

### **6.1.3 Product Storage and Stability**

Investigational product will be stored according to FDA-approved prescribing information (Store at 20° to 25°C (68° to 77°F). Excursions permitted to 15° – 30°C (59° – 86°F)).

### **6.1.4 Preparation**

In accord with FDA-approved prescribing information, ferumoxytol injection will be administered as an intravenous infusion in 50-200 mL 0.9% Sodium Chloride Injection, USP or 5% Dextrose Injection, USP over at least 15 minutes.

### **6.1.5 Dosing and Administration**

In accord with FDA-approved prescribing information, ferumoxytol injection will be administered as an initial 510 mg dose followed by a second 510 mg dose 3 to 8 days later. Once added to intravenous infusion bags containing either 0.9% Sodium Chloride Injection, USP (normal saline), or 5% Dextrose Injection, USP, at concentrations of 2-8 mg elemental iron per mL, the investigational product will be used immediately but may be stored at controlled room temperature (25°C ± 2°C) for up to 4 hours.

### **6.1.6 Route of Administration**

The investigational product will be administered by intravenous infusion.

### **6.1.7 Dose Adjustments/Modifications/Delays**

Dosing may be discontinued due to intolerance, patient request, or protocol non-adherence. Modifications/Delay of dose outside of the FDA-approved prescribing information is not permitted.

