## Schematic of Study Design

## Schedule of Assessments

| Visit Name                  | Screening   | First Dose Ferumoxytol injection | Second Dose Ferumoxytol injection
(3-8 days after first dose) |
|-----------------------------|-------------|----------------------------------|--|
| Visit Number                | 1           | 2                                | 3  |
| Study Week ( $\pm 7$ days)* | 0           | 0-2                              | 1-3  |
| Informed consent            | X           |                                  |  |
| Screening Evaluation        | X           |                                  |  |
| Medical History             | X           | X                                | X  |
| Bleeding/Blood History      | Transfusion | X                                | X  |

CONFIDENTIAL

This material is the property of the NYU School of Medicine and Langone Medical Center. Do not disclose or use except as authorized in writing by the study sponsor  
Interventional Template Version: 28 APR 2017

|                                |           |   |   |
|--------------------------------|-----------|---|---|
| Vital Signs                    | X         | X | X |
| Cardiovascular exam            | X         | X | X |
| VAD settings                   | X         | X | X |
| Ferumoxytol
Administration* | injection | X | X |
| Infusion Monitoring            |           | X | X |
| AE monitoring                  |           | X | X |
| Concomitant Meds               | X         | X | X |

\*Ferumoxytol injection will be administered according to FDA-approved prescribing instructions 3-8 days apart

CONFIDENTIAL

This material is the property of the NYU School of Medicine and Langone Medical Center. Do not disclose or use except as authorized in writing by the study sponsor  
Interventional Template Version: 28 APR 2017

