### 3.1 Primary Objective

To assess feasibility of iron-repletion with ferumoxytol injection (initial 510 mg dose followed by a second 510 mg dose 3 to 8 days later, each dose infused over at least 15 minutes while the patient is in a reclined or semi-reclined position) in iron-deficient patients with durable ventricular assist device support.

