### **5.7 Participant Withdrawal or Termination**

#### **5.7.1 Reasons for Withdrawal or Termination**

CONFIDENTIAL

This material is the property of the NYU School of Medicine and Langone Medical Center. Do not disclose or use except as authorized in writing by the study sponsor  
Interventional Template Version: 28 APR 2017

Participants are free to withdraw from participation in the study at any time upon request. An investigator may terminate participation in the study if:

- Any clinical adverse event (AE), laboratory abnormality, or other medical condition or situation occurs such that continued participation in the study would not be in the best interest of the participant
- The participant meets an exclusion criterion (either newly developed or not previously recognized) that precludes further study participation
- The participant is not able to return for the second dose of ferumoxytol within 15 days of the first dose.

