### **6.1.8 Duration of Therapy**

Participants will receive the FDA-approved regimen of two doses of ferumoxytol injection (an initial 510 mg dose followed by a second 510 mg dose 3 to 8 days later).

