### **7.3 Study Schedule**

Study visits will occur within a time window  $\pm 7$  days of the times listed in this section.

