### 7.3.3 Final Study Visit

#### Enrollment/Baseline Visit (Visit 3, Day 3-8)

- Verify informed consent documentation.
- Verify inclusion/exclusion criteria.
- Assess for interim changes in clinical status or concomitant medications.
- Record VAD settings, seated vital signs (mean blood pressure, heart rate, oxygen saturation) and cardiovascular examination.
- Obtain urine or blood pregnancy test in women of childbearing potential.
- Record vital signs and assess clinical stability of subject.
- Administer the study treatment as described with monitoring for hypersensitivity reactions.
- Report status of iron repletion to clinical care team.

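### The ±7-day visit window (7.3) conflicts with the ban on dose delay (6.1.7), and the primary endpoint does not say how a second dose on Day 9-15 is scored

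*Combined protocol and SAP*

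**What the plan says.** **The interval between doses.** The primary objective (3.1) describes an "initial 510 mg dose followed by a second 510 mg dose 3 to 8 days later". Section 6.1.5 repeats this ("followed by a second 510 mg dose 3 to 8 days later") as the prescribing-information regimen. Section 6.1.8 says "Participants will receive the FDA-approved regimen of two doses of ferumoxytol injection" and gives the same 3 to 8 days. Section 6.1.7 adds that "Modifications/Delay of dose outside of the FDA-approved prescribing information is not permitted".

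**The visit window.** Section 7.3 opens with "Study visits will occur within a time window" of ±7 days around the times it lists, and makes no exception. One of those times is the second-dose visit in 7.3.3, headed "Enrollment/Baseline Visit (Visit 3, Day 3-8". In the Schedule of Assessments, the study-week row that carries the ±7 days also carries an asterisk. Its footnote reads "Ferumoxytol injection will be administered according to FDA-approved prescribing instructions 3-8 days apart".

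**The termination criterion.** Under 5.7.1 an investigator may end participation if "The participant is not able to return for the second dose of ferumoxytol within 15 days of the first dose".

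**The endpoint.** Sections 4.2.1 and 9.4.1 define the primary outcome as completing treatment in accordance with the study protocol. Neither states an interval. Section 9.2 makes this the only hypothesis tested; safety and exploratory outcomes are descriptive. Section 13.3 defines a deviation as any noncompliance with the protocol and refers to a Manual of Procedures for further handling. It does not say whether a deviation makes a participant a non-completer.

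**The concern.** When an endpoint is defined as adherence to the protocol, the protocol has to give one answer on what adherence is. Here a second dose on, say, Day 11 satisfies the visit window in 7.3 and breaches the dosing rule in 6.1.7. Two careful analysts could score the same participant differently, each citing protocol text.

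This affects the one tested outcome, and also the figure the pilot is meant to supply for planning later trials. The study is open-label and 7.1.1 has the date and time of each infusion recorded. Unless the rule is written down beforehand, it could be chosen with the dates in view.

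**Working it through.** **1. The window.** Visit 3 is listed at Day 3-8 (7.3.3) and the allowance is ±7 days (7.3).
- Latest day: 8 + 7 = Day 15, the same limit as in 5.7.1.
- Earliest day, read literally: 3 − 7 = Day −4, before the first dose.

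**2. Fit with total visit duration.** Section 7.3.1 allows screening up to 14 days before the first dose, and 5.5 gives 1-3 weeks (up to 21 days) for the three visits.
- Second dose by Day 8: 14 + 8 = 22 days, about 3 weeks.
- Second dose by Day 15: 14 + 15 = 29 days, more than 4 weeks.

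**3. The plan's own power figure.** Inputs from 9.4.2 and 9.5: n = 20, null 0.75, one-tailed alpha 0.05, alternative 0.40. With X the number of completers:
- P(X ≤ 11 | 0.75) = 0.0409 and P(X ≤ 12 | 0.75) = 0.1018, so the exact test rejects at 11 or fewer.
- Power at 40%: P(X ≤ 11 | 0.40) = 0.943.

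The stated power above 80% is reproduced. It is not in question here.

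**4. The boundary under the planned chi-square test.** Expected counts are 15 and 5, so chi-square = (x − 15)²/15 + (x − 15)²/5 = (x − 15)²/3.75.

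| Completers | Chi-square | One-tailed p | With continuity correction | Exact p |
|---|---|---|---|---|
| 11/20 (55%) | 16/3.75 = 4.267 | 0.019 | 0.035 | 0.041 |
| 12/20 (60%) | 9/3.75 = 2.400 | 0.061 | 0.098 | 0.102 |

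All three versions put the cut between 11 and 12.

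**5. Effect of one late dose.** Each reclassified participant moves the proportion by 1/20 = 5 points.
- 18/20 (90%) becomes 17/20 (85%): exact p = 0.976 and 0.909, neither rejecting.
- 12/20 becomes 11/20: the result changes from not rejected to rejected.
- In general, with x ≥ 12 dosed by Day 15, it takes x − 11 late doses to reverse the test: one if x = 12, four if x = 15, seven if x = 18.

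**6. How often the two scorings disagree.** The documents give no late-dose rate, so the rates below are assumptions. Let d be the probability of receiving the second dose by Day 15 and f the share of those doses given after Day 8, with participants independent. The number scored complete when late doses fail can never exceed the number when they count. Hence

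P(opposite results) = P(X ≤ 11 | 20, d(1 − f)) − P(X ≤ 11 | 20, d).

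| Dosed (d) | Late share (f) | Calculation | P(opposite results) |
|---|---|---|---|
| 90% | 5% | 0.00104 − 0.00006 | 0.1% |
| 90% | 10% | 0.00707 − 0.00006 | 0.7% |
| 80% | 5% | 0.0320 − 0.0100 | 2.2% |
| 80% | 10% | 0.0784 − 0.0100 | 6.8% |
| 75% | 10% | 0.169 − 0.041 | 12.8% |

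**The case against.** The best reply is that the natural reading already settles the matter. The 3 to 8 days appear in the summary, the objective, the dosing sections, the procedures and the schedule, and 6.1.7 is an express prohibition. A specific dosing rule would ordinarily outrank a general line about visit windows. The Day −4 edge suggests that 7.3 is generic wording, and the asterisk in the schedule leads back to 3-8 days. The arithmetic in step 2 points the same way. Section 5.7.1 is discretionary and concerns staying in the study; it does not authorise a dose. On this view a late dose is simply not completion according to the protocol.

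Most of this is fair, and it shows which way the text leans. It does not remove the conflict: 7.3 is also protocol text, has no exception, and lists Visit 3. The reply also gets only as far as calling a late dose a deviation. That a deviation means non-completion remains an inference.

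Two further points stand in part. Section 13.3 sends details of deviation handling to the Manual of Procedures, which is not among the documents. So the claim is limited to this: the protocol and SAP do not fix the scoring. A manual cannot be presumed to resolve a contradiction in the protocol it serves. Second, the effect on the test is small when nearly everyone is dosed on time, as step 6 shows, and the 12-versus-11 example was chosen because it sits on the boundary.

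**Conclusion.** The concern holds. The visit window and the dosing rule contradict each other for a second dose on Day 9-15, and the only tested endpoint depends on which governs. The firm consequence is a 5-point shift in the reported completion proportion for each such dose, if any occur, taking the denominator as the 20 planned participants, who are not replaced on withdrawal (5.6, 5.7.2). The effect on the test is conditional. It needs the count to cross from 12 to 11, with probability between 0.1% and 6.8% for 80-90% dosed and 5-10% late, and 12.8% at 75% dosed and 10% late. Those rates are assumed. With high, punctual dosing the conclusion will rarely change, but the feasibility estimate will. The sample size and stated power are unaffected. This should be fixed, though it does not undermine the design.

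**What to change.** - Reconcile 5.7.1, 6.1.5, 6.1.7, 6.1.8, 7.3 and the Schedule of Assessments to one stated interval between doses, and say explicitly whether the ±7 days applies to Visit 3. Which interval is right is for the sponsor and investigator to decide.
- In 4.2.1 and 9.4.1, define completion by that interval, and say whether a dose-timing deviation under 13.3 counts as non-completion.
- Report the second dose in three rows: given within the reconciled interval, given outside it, not given. Readers can then see the proportion under either scoring.

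The cost is one amendment of wording and one short table. Infusion dates and times are already collected (7.1.1), so no visits, procedures or participants are added.

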### **6.1.8 Duration of Therapy**

Participants will receive the FDA-approved regimen of two doses of ferumoxytol injection (an initial 510 mg dose followed by a second 510 mg dose 3 to 8 days later).

### **6.1.9 Tracking of Dose**

Study drug will be administered under supervision of research personnel at the NYU CTSI. The investigational product will be ordered in the EPIC medical record by the principal investigator and will be dispensed according to the protocol by the NYU Research Pharmacy.

CONFIDENTIAL

This material is the property of the NYU School of Medicine and Langone Medical Center. Do not disclose or use except as authorized in writing by the study sponsor  
Interventional Template Version: 28 APR 2017

## **6.2 Study Agent Accountability Procedures**

The investigational product will be sent by AMAG pharmaceuticals to the NYU Research Pharmacy and stored according to instructions in the FDA-approved prescribing information. Drug accountability logs will be maintained by the NYU Research Pharmacy. Unused investigational product will be returned to AMAG pharmaceuticals or disposed according to NYU Research Pharmacy protocol.

# **7 Study Procedures and Schedule**

## **7.1 Study Procedures/Evaluations**

### **7.1.1 Study Specific Procedures**

Study visits (See Attached Study Schematic Figure and Schedule of Assessments Table): The study will require 3 visits over approximately 2 weeks for each subject.

- Visit 1: Informed consent and screening\*
- Visit 2: First dose of ferumoxytol injection Study Drug\*
- Visit 3: Second dose of ferumoxytol injection Study Drug

\*Visits 1 and 2 may occur on the same day.

Screening procedures. After the informed consent form is signed, chart review and patient interview will be performed to determine eligibility. Screening will include subject interview and chart review to determine eligibility. Clinical information on co-morbid conditions, VAD settings, and concomitant medications will be collected. Vital signs in the seated position and a brief cardiovascular exam will be recorded. Women of childbearing potential will undergo urine or blood pregnancy testing.

Study Drug Administration: Ferumoxytol injection will be administered to eligible subjects according to FDA-approved prescribing information. Prior to administration, interim history, concomitant medications, VAD settings, vital signs and a cardiovascular exam will be recorded. Two doses of ferumoxytol injection will be administered: an initial 510 mg dose followed by a second 510 mg dose 3 to 8 days later, each dose given as an intravenous infusion in 50-200 mL 0.9% Sodium Chloride Injection, USP or 5% Dextrose Injection, USP while the subject is in a reclined or semi-reclined position. Subjects will be observed for signs or symptoms of hypersensitivity reactions (including monitoring of blood pressure and pulse rate) during and for at least 30 minutes after ferumoxytol injection administration. The dose, date and time of infusion, duration of infusion, and treatment-related adverse effects (diarrhea, nausea, dizziness, hypotension, hypersensitivity) will be recorded.

### Clinical Data Collection for Research

Laboratory data. Clinical blood test results (serum ferritin, transferrin saturation, and hemoglobin) before administration of ferumoxytol injection and from 2-24 weeks after administration of ferumoxytol injection will be recorded by medical chart review.

Bleeding/Transfusion data. Information on bleeding events (source of bleeding, need for hospitalization, intervention(s)) and number of blood transfusion for 2-24 weeks after treatment will be collected from medical chart review.

CONFIDENTIAL

This material is the property of the NYU School of Medicine and Langone Medical Center. Do not disclose or use except as authorized in writing by the study sponsor  
Interventional Template Version: 28 APR 2017

Six-minute walk test. The six-minute walk test is routinely performed in VAD patients for clinical assessment of functional capacity. Results will be obtained by medical chart review.

### **7.1.2 Standard of Care Study Procedures**

The only research procedure that differs from standard of care procedures is the administration of ferumoxytol injection, since this intravenous iron preparation is not available on the NYULH formulary. Iron-deficient VAD patients not participating in this study would be referred to outpatient infusion centers to receive other formulations of intravenous iron that require a greater number of visits for iron repletion. The risks associated with ferumoxytol injection are comparable to the known risks of other FDA-approved intravenous iron preparations on the formulary at NYULH.

VAD patients routinely undergo laboratory testing for iron-deficiency anemia and serial assessment of submaximal exercise capacity with 6-minute walk testing as part of standard of care.

## **7.2 Laboratory Procedures/Evaluations**

There are no research laboratory procedures or evaluations.

### **7.3 Study Schedule**

Study visits will occur within a time window  $\pm 7$  days of the times listed in this section.

#### **7.3.1 Screening**

##### **Screening Visit (Visit 1, Day -14 to 0)**

- Obtain informed consent of potential participant verified by signature on written informed consent for screening form.
- Review medical history to determine eligibility based on inclusion/exclusion criteria.
- Record concomitant medications
- Record VAD settings, seated vital signs (mean blood pressure, heart rate, oxygen saturation) and cardiovascular examination.
- Schedule study visits for participants who are eligible and available for the duration of the study. If the participant is eligible to receive Ferumoxytol injection, the first administration of study drug may be completed on the same day as the screening visit.
- Obtain urine or blood pregnancy test in women of child-bearing potential.
- Provide participants with instructions for the return for the infusion of Ferumoxytol injection .

#### **7.3.2 Enrollment/Baseline**

##### **Enrollment/Baseline Visit (Visit 2, Day 0)**

- Verify informed consent documentation.
- Verify inclusion/exclusion criteria.

CONFIDENTIAL

This material is the property of the NYU School of Medicine and Langone Medical Center. Do not disclose or use except as authorized in writing by the study sponsor  
Interventional Template Version: 28 APR 2017

- Assess for interim changes in clinical status or concomitant medications.
- Record VAD settings, seated vital signs (mean blood pressure, heart rate, oxygen saturation) and cardiovascular examination.
- Obtain urine or blood pregnancy test in women of childbearing potential (if visit is occurring >1 day after screening visit).
- Record vital signs and assess clinical stability of subject.
- Administer the study treatment as described with monitoring for hypersensitivity.
- Provide participants with instructions for the return for the infusion of Ferumoxytol injection .

### 7.3.3 Final Study Visit

#### Enrollment/Baseline Visit (Visit 3, Day 3-8)

- Verify informed consent documentation.
- Verify inclusion/exclusion criteria.
- Assess for interim changes in clinical status or concomitant medications.
- Record VAD settings, seated vital signs (mean blood pressure, heart rate, oxygen saturation) and cardiovascular examination.
- Obtain urine or blood pregnancy test in women of childbearing potential.
- Record vital signs and assess clinical stability of subject.
- Administer the study treatment as described with monitoring for hypersensitivity reactions.
- Report status of iron repletion to clinical care team.

### 7.3.4 Withdrawal/Early Termination Visit

There will be no visit required for early termination. Participants will be asked to provide permission for continued access to their medical record for 6 months.

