| Endpoint                             | 
Primary Feasibility Outcome: Proportion of subjects who complete ferumoxytol injection therapy according to the study protocol.
 
Primary Safety Outcome: Incidence of treatment related adverse events
 
Other Exploratory Outcomes based on clinically available data obtained by review of the medical record:
 

• Change from pre-treatment baseline in serum ferritin 1-24 weeks after ferumoxytol injection therapy

• Change from pre-treatment baseline in transferrin saturation 1-24 weeks after ferumoxytol injection therapy

• Change from pre-treatment baseline in hemoglobin level 1-24 weeks after ferumoxytol injection therapy

• Change from pre-treatment baseline in 6-minute walk distance 1-24 weeks after ferumoxytol injection therapy

 |
| Study Duration                       | Total anticipated duration of study (subject accrual, completion of study therapy and assessments, data analysis, manuscript preparation) is 18 months.  |
| Participant Duration                 | Six months including three study visits over about two weeks, and data extraction from medical record for up to six months after ferumoxytol injection.  |
| Duration of IP administration        | Two doses of ferumoxytol injection will be administered intravenously 3-8 days apart.  |
| Population                           | Adult subjects with stable clinical status after clinically-indicated VAD placement and iron deficiency anemia will be enrolled  |
| Study Sites                          | NYULH is the only clinical site for enrollment and study procedures  |
| Number of participants               | 20 subjects from the NYULH VAD program will be enrolled  |
| Description of Study Agent/Procedure | Ferumoxytol injection will be administered to eligible subjects according to FDA-approved prescribing information. Two doses of ferumoxytol injection will be administered: an initial 510 mg dose followed by a second 510 mg dose 3 to 8 days later, each dose given as an intravenous infusion in 50-200 mL 0.9% Sodium Chloride Injection, USP or 5% Dextrose Injection, USP while the subject is in a reclined or semi-reclined position.   |
| Reference Therapy                    | There is no reference therapy for this study   |

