### **5.5 Duration of Study Participation**

The study will require active participation at three visits conducted over 1-3 weeks. The screening visit and first injection of study drug may occur on the same day. Clinical data from the medical record will be reviewed and entered in the research database for 6 months. There are no study procedures other than data collection from medical record after completion of the two visits for study drug infusion.

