### **5.7.2 Handling of Participant Withdrawals or Termination**

Withdrawn or terminated participants will be followed for extraction of clinical data from the medical record for 6 months with participant permission. Since the primary outcome is feasibility, there will be no replacement of withdrawn subjects.

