### **9.3 Analysis Datasets**

Feasibility analysis dataset. Intention to treat (ITT) will be defined as all patients who provide consent and are eligible to receive study treatment. The ITT data set will be used for the primary feasibility endpoint.

Safety objective and exploratory objectives analysis dataset. All eligible subjects who received any study drug, and for whom post-dose data are available, will be included in the safety and exploratory objectives analysis set.

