### **12.4 Participant and Data Confidentiality**

All patient data will be kept strictly confidential, except when published for purposes of reporting data. In that case, the patients are never identified. All electronic data will be de-identified and transmitted and stored with secure systems that meet or exceed Federal guidelines (REDCap). The Principal Investigator will maintain files with identifying information in a locked cabinet in a locked room or in password-protected files on a password-protected computer. No vulnerable subject populations will be enrolled in this study.

Information about study subjects will be kept confidential and managed according to the requirements of the Health Insurance Portability and Accountability Act of 1996 (HIPAA). Those regulations require a signed subject authorization informing the subject of the following:

- What protected health information (PHI) will be collected from subjects in this study
- Who will have access to that information and why
- Who will use or disclose that information
- The rights of a research subject to revoke their authorization for use of their PHI.

In the event that a subject revokes authorization to collect or use PHI, the investigator, by regulation, retains the ability to use all information collected prior to the revocation of subject authorization. For subjects that have revoked authorization to collect or use PHI, attempts should be made to obtain permission to collect at least vital status (i.e. that the subject is alive) at the end of their scheduled study period.

Participant confidentiality is strictly held in trust by the participating investigators, their staff, and the sponsor(s) and their agents. No information concerning the study or the data will be released to any unauthorized third party without prior written approval of the sponsor.

CONFIDENTIAL

This material is the property of the NYU School of Medicine and Langone Medical Center. Do not disclose or use except as authorized in writing by the study sponsor  
Interventional Template Version: 28 APR 2017

The representatives of the IRB or other governmental regulatory office may inspect all documents and records required to be maintained by the investigator, including but not limited to, medical records (office, clinic, or hospital) and pharmacy records for the participants in this study. The clinical study site will permit access to such records.

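### Making chart follow-up depend on permission after investigator termination can selectively remove dosed non-completers from the exploratory and later safety data

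*Combined protocol and SAP*

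**What the plan says.** The general rule, in Section 5.5, is "Clinical data from the medical record will be reviewed and entered in the research database for 6 months". The Protocol Summary gives the same horizon as part of participant duration: "data extraction from medical record for up to six months after ferumoxytol injection". Neither place attaches a further condition.

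For people who stop early, Section 5.7.2 says "Withdrawn or terminated participants will be followed for extraction of clinical data from the medical record for 6 months with participant permission". Section 7.3.4 requires no early-termination visit and then says "Participants will be asked to provide permission for continued access to their medical record for 6 months".

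Section 5.7.1 distinguishes participants who withdraw at their own request from those stopped by the investigator ("An investigator may terminate participation in the study if" introduces that list). The investigator's grounds are an adverse event or other condition that makes continuing unsuitable, an exclusion criterion newly met or newly recognised, and inability to return for the second dose within the stated limit. Sections 5.7.2 and 7.3.4 do not carry the distinction forward.

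Section 9.3 defines the safety and exploratory set as "All eligible subjects who received any study drug, and for whom post-dose data are available". Section 12.4 covers revocation of authorization: the investigator "retains the ability to use all information collected prior to the revocation of subject authorization", and permission should be sought to collect at least vital status.

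**The concern.** After the second infusion the study consists only of record review. For a subject stopped after dose 1, the chart is therefore the only source of the changes in ferritin, transferrin saturation, hemoglobin and walk distance (Section 4.2.3) and of the bleeding and transfusion data (Section 7.1.1). Making the chart conditional for this group, and not for completers, puts the risk of missing data on non-completers alone.

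The loss may also be related to outcome. Active bleeding and recent hospitalization are exclusion criteria (Section 5.2). Eligibility is re-verified at Visit 3 (Section 7.3.3), and a newly met exclusion is a ground for termination. Bleeding and hospitalization are also among the things the chart review is meant to describe (Protocol Summary, exploratory objectives). A subject who bleeds between doses can thus be terminated for that event, after which later chart data need permission.

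Section 9.2 says these estimates are meant to inform planning of later trials. No method for missing data is given, withdrawn subjects are not replaced (5.7.2), and 20 are enrolled to give 20 evaluable (5.6). Any loss moves the summaries toward completers only.

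**Working it through.** **1. The passages side by side.**

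| Situation | Chart extraction | Section |
|---|---|---|
| Every subject | six months, no condition stated | 5.5, Protocol Summary |
| Withdrew at own request | six months, with permission | 5.7.2, 7.3.4 |
| Terminated by the investigator, consent not withdrawn | six months, with permission | 5.7.2, 7.3.4 read with 5.7.1 |
| Revoked authorization | earlier data usable; vital status sought | 12.4 |

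The third row is the problem: it treats someone who merely stopped drug like someone who asked to leave. Under 9.3, a dosed subject in that row with no post-dose data leaves the set. One whose only post-dose data are infusion-visit observations still contributes nothing to the change endpoints.

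**2. The plan's own completion rates.** Section 9.5 gives n = 20, null 0.75, alternative below 0.40, one-tailed alpha 0.05 and power above 80%. The exact lower-tail binomial test rejects at 11 or fewer completers:
- size: P(X ≤ 11 | 20, 0.75) = 0.0409 (a cut-off of 12 would give 0.1018);
- power: P(X ≤ 11 | 20, 0.40) = 0.9435.

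The stated power is reproduced. The two rates serve below as benchmarks, not forecasts.

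**3. Ceiling on the number lost.** Assume that every non-completer received dose 1 and was withdrawn or terminated. The documents give no refusal or non-contact rate, so the share lost runs from 0 to 100%.
- 75% completion: 20 × 0.25 = 5 non-completers, so 0 to 5 of 20 lost (0 to 25%).
- 40% completion: 20 × 0.60 = 12 non-completers, so 0 to 12 of 20 lost (0 to 60%).

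**4. Effect on mean hemoglobin change.** Assumptions: completers gain 1.0 g/dL with SD 1.2, close to the ferumoxytol arms of Table I in Section 2.4.2 (mean changes 0.82, 1.22 and 1.02; SDs 1.24, 1.25 and 1.13). One-dose subjects gain d = 0 to 0.5 g/dL, a range with no source in the documents. Let f be the non-completer fraction and r the share of them lost.

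- Mean over all dosed: (1 − f) × 1.0 + f × d
- Mean observed: [(1 − f) × 1.0 + f(1 − r)d] / [(1 − f) + f(1 − r)]

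| f | r | All dosed (d = 0; 0.5) | Observed (d = 0; 0.5) | Overstatement, g/dL |
|---|---|---|---|---|
| 0.25 | 0.5 | 0.750; 0.875 | 0.857; 0.929 | 0.11; 0.05 |
| 0.25 | 1 | 0.750; 0.875 | 1.000; 1.000 | 0.25; 0.13 |
| 0.60 | 1 | 0.400; 0.700 | 1.000; 1.000 | 0.60; 0.30 |

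**5. Relative to the standard error of the data analysed.**
- n = 15: SE = 1.2/√15 = 0.310. Then 0.125/0.310 = 0.40 and 0.25/0.310 = 0.81.
- n = 8: SE = 1.2/√8 = 0.424. Then 0.30/0.424 = 0.7 and 0.60/0.424 = 1.4.
- Precision: five lost raises the SE by √(20/15) = 1.155, about 15%.

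**6. Primary endpoint.** Under 9.3 it is analysed in all consented, eligible subjects, and a missed infusion is itself the observed result. Loss: zero in every case.

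**The case against.** A reader might infer that the plan defines the end of follow-up in three rival ways. It does not. The horizon is six months throughout, and 5.7.2 can be read as a specific provision beside the general rule in 5.5. Section 12.4 sets no end date; it says what may be used or sought after revocation.

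A reader might also infer that non-completers lose their data by rule. That is too strong. The default in 5.7.2 is that these participants are followed, and loss needs a refusal or a failed contact. The text does not say when permission is asked, and the consent form is not in the copy reviewed, so the original consent may already cover continued access. Nor does the absence of a termination visit mean no chance to ask: these patients see a dedicated VAD team regularly (Section 5.4), and Section 8.3 requires unresolved adverse events to be followed.

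The numbers are ceilings. Termination is at the investigator's discretion, some non-completers may never be terminated or never dosed, and 75% and 40% are test values. The affected summaries are descriptive, in a 20-subject single-arm pilot using routine-care data. Asking permission is a defensible way to protect participants.

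All of this limits the size of the point. It does not explain why someone stopped for an adverse event or a missed dose, who has not asked to leave, should face a condition that completers do not. If the original consent already covers access, the request in 7.3.4 is unnecessary and still creates an avoidable route to loss.

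**Conclusion.** The concern holds in limited form. The plan does not separate stopping study drug from withdrawing consent, so selective loss of exploratory chart data is possible among dosed subjects who stop early. Later safety information is exposed too: Section 8.3 ties its 7-day and 30-day recording windows to the last day of participation, which termination may bring forward. Adverse events already recorded at the infusion visits are not lost.

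The actual loss cannot be estimated from the documents. The five-subject case in the working is an upper bound at 75% completion, and its hemoglobin bias rests on the assumed responses and on every non-completer being dosed, terminated and lost. The direction depends on one-dose subjects gaining less than completers. The feasibility result is untouched, so this is an inexpensive improvement to secondary and exploratory data, not a flaw in the main analysis.

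**What to change.** In Sections 5.7.1, 5.7.2 and 7.3.4, separate three events: discontinuation of study drug, withdrawal from the study, and revocation of authorization (aligned with 12.4). State that:

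- subjects who stop drug without withdrawing consent stay in six-month record extraction under the original consent and authorization unless they revoke it;
- only those who ask to leave the study are asked whether this includes record access;
- the number lost to record follow-up is reported, with reasons.

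Suitable text for 7.3.4: *Participants who stop study drug remain in record follow-up. A participant who asks to withdraw from the study will be asked whether this includes record access.*

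In the same amendment, reconcile Section 13.1 with Section 5.5. The former destroys the link between study code and identity once study procedures are complete; the latter needs six months of chart extraction after the last infusion. Unless record review counts as a study procedure, extraction could be blocked for completers as well.

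The cost is protocol wording, one sentence in the consent form and a routine IRB amendment, with no added visits, tests or patients. The consent form must say plainly that record review continues after stopping drug unless the participant objects. No dosing or stopping rule changes.
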